8. MANAGEMENT OF THE DATA

The collected data will be managed into a dedicated electronic dedicated case report form (eCRF). Only the Investigators will have access to the data with a personal password to enter in the eCRF. . Only the PI and the first data manager will be able to see all the data, while the other investigators will have permission to manage only the data of the patients enrolled in their center.

To ensure the correct data collection two Investigators will perform the clinical and radiological assessment at each follow-up visit. Before the conclusion of the visit, a double-check will be performed by the Investigators. The CRF will be completed at the time of enrollment and each follow-up visit thereafter.

A personal code will be generated at the enrollment. The CRF will be filled anonymously. The following anamnestic data: age, sex, comorbidities (hypertension, cardiopathy, hyperlipidemia, peripheral arterial disease, previous surgery, etc). Procedure planning details were detailed previously. The procedure details: planned and unplanned adjunctive procedure, the adverse events, the skin-to-skin time, the fluoroscopy time and DAP, the type of anesthesia, the dose, and characteristics of CM used. Primary and secondary endpoints will be registered as defined previously.

The following indicators will also be collected: time of recovery from the intervention and the number of an hour passed in the Intensive Care Unit if needed.

In case of the patient's voluntary withdrawal, the CRF will be discontinued. The patient will undergo standard clinical practice follow-up.

In case of device-related adverse-events, a detailed description of the event will be performed to inform the regulatory authority. The clinical follow-up and the CRF proceed as stated.

In case of death, the study personnel will investigate the cause and any eventual relation with the treatment or device will be declared to the regulatory authority and carefully reported on the eCRF.

Statistical methods

Continuous variables are expressed as mean, and standard deviation and differences were tested with the two-sided t-test or the Mann–Whitney U-test, if appropriate. Categorical variables are expressed as counts and percentages and the chi-square test or Fisher's exact test was used for analysis. All data were entered into the logistic regression model if they had a univariable P-value of <0.05. Data resulted significant in this model were put in a multivariate one. In the multivariable analyses, clinical factors or potential confounding variables were expressed as odds ratio with 95% confidence interval (CI). The goodness of fit of the logistic regression models has been assessed calculating the C-statistic. Patency rate and freedom from adverse events were assessed through the Kaplan-Meier analysis with their relative 95% CI. The analysis was carried out using STATA 15.1 (StataCorp College Station, Texas, USA).

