- Freedom from procedure related Adverse events. Adverse events are defined as any systemic or local complication directly related to the procedure. Adverse events that occurred in the first 30-day were considered procedure-related, unless differently demonstrated.
- Freedom from procedure related re-intervention. Any surgical, open, or endovascular, procedure aimed to address adverse events was named re-intervention.
- Quality of life improvement;
- Analysis of anatomical and preoperative factors afflicting the primary outcomes.

The secondary endpoints represent specific technical aspects related to the procedure and the endograft.

Treatment-related adverse events and re-interventions are important to state the safety of the procedure over time and its external reproducibility.

Timeline

Months 1-3 Organization and logistic set-up.

[figure not shown]
Months 3-15 Subjects enrollment, data collection, treatments, clinical follow-up.

Months 15-18 Conclusion of recruitment, first (3 months) follow-up end for every patient, ad-interim analysis

Month 15-36 12-months follow-up end, mid-term analysis

Month 63-75 Conclusion of the follow-up, analysis of the results and their validation, statistical analysis, project completion and analysis for further work, dissemination of the results

Gantt chart:

Sample size

No statistical analysis of the sample size was carried out. Considering the number of AIOD responding to the inclusion criteria treated in the participating centers and the enrollment period (1 year) a sample size of 100 patients was estimated. This number should be sufficient to evaluate the endpoints reported above.

Recruitment

All patients affected by AIOD responding criteria for endovascular treatment were evaluated at the Vascular Surgery Unit of the Azienda Ospedaliero Universitaria di Modena and the other participating centers. Those meeting the inclusion criteria will be singularly recruited.

Taking into account a mean of 100 endovascular procedures for the treatment of complex AIOD (TASC C and D lesions involving aortic bifurcation and or the first 5mm of one of both common iliacs) a safety 12-month recruitment should be considered. The entire Medical staff of the department is informed about the present project and will refer the potential subjects to the Investigators.

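### Factors affecting patency are picked by P-value from about 25 candidates, in a logistic model that ignores follow-up time; a short prespecified Cox model would be more reliable

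*Combined protocol and SAP*

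**What the plan says.** Section 7 (Secondary endpoints) includes "Analysis of anatomical and preoperative factors afflicting the primary outcomes". The primary endpoint in the same section is patency of three types (primary, assisted, secondary), each at short, middle and long term.

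Section 8 (Statistical methods) gives one route from candidates to reported factors. The first step is "All data were entered into the logistic regression model if they had a univariable P-value of <0.05"; the next is "Data resulted significant in this model were put in a multivariate one". Results are given as odds ratios. The section does not name the dependent variable, the time point, the second threshold or a candidate list. It also does not say whether the first model is joint or one variable at a time.

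For patency itself the same section says "Patency rate and freedom from adverse events were assessed through the Kaplan-Meier analysis with their relative 95% CI". No Cox model or other regression for censored data appears anywhere in the document.

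On incomplete follow-up, section 8 says "In case of the patient's voluntary withdrawal, the CRF will be discontinued". Section 7 (Follow-up) says that patients who withdraw go on being examined and imaged in routine care. Section 8 also has deaths investigated and recorded on the eCRF. None of these statements says how such patients enter the factor model.

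**The concern.** There are two problems, and the first is the larger.

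**Selection.** Many candidates are tested against few events, and only those that pass are reported. Chance factors get through. A real factor of moderate size passes mainly in samples where its estimate happens to be high. Readers could then take an anatomical predictor as established when it is noise or is overstated.

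**Time.** Kaplan-Meier treats a patient who dies or withdraws while patent as censored. Logistic regression needs a yes or no. Counting such patients as patent and dropping them bias a factor that is related to death in opposite directions, and the plan does not choose between them.

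**Working it through.** The plan states no event count, event rate or candidate count for this analysis, and section 7 says that the sample of 100 was not derived statistically. There is therefore no figure to reproduce, and the inputs below are assumptions unless a source is given.

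**1. Candidates** (sections 7 and 8, data collected). Seven diameters (D1 to D6 and access artery); five lengths (L2, L4, L5, L6, lesion); calcium, thrombus, iliac stenosis and TASC class (4); Rutherford, WIfI and ABI (3); age, sex and four comorbidities (6). Total 7 + 5 + 4 + 3 + 6 = 25. Adding peripheral arterial disease and aortic stenosis gives 27.

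**2. Screen alone, independent null candidates.** Expected false passes: 25 × 0.05 = 1.25. Chance of at least one: 1 − 0.95^25 = 72%. For three prespecified factors: 1 − 0.95^3 = 14%.

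**3. The whole rule, by simulation.** 2,000 runs per setting, n = 100, 25 null candidates (19 continuous, 6 binary), t-test or Fisher screen, equal correlation within the blocks of 7, 5, 4 and 3, patient factors independent. Reading A: joint logistic model on the screened factors, keep P<0.05, refit. Reading B: univariable logistic P<0.05, then a joint model. Entries are the percentage of trials with at least one null factor, at 12 / 24 / 35 events. The last two columns count null factors with P<0.05 in the final model.

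| Correlation | Screen alone | Reading A | Reading B |
|---|---|---|---|
| 0 | 70 / 69 / 70 | 61 / 63 / 66 | 62 / 64 / 66 |
| 0.5 | 59 / 64 / 63 | 44 / 51 / 50 | 45 / 52 / 51 |
| 0.7 | 57 / 58 / 56 | 36 / 44 / 42 | 38 / 45 / 43 |

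A prespecified three-factor model gives 11 to 14% throughout. Monte Carlo SE is about 1 point. Separate simulations of reading A at correlation 0.7 and 24 events gave 38 to 39%, so that row depends somewhat on set-up but stays within 36 to 45%.

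**4. Overstatement, about 24 events.** A true OR of 1.5 per SD is kept in 24 to 40% of trials. Its median OR when kept is 1.81 to 1.98, against 1.53 to 1.55 if prespecified. For a true OR of 2.0 the kept median is 2.04 to 2.36 against 2.06, so the low end shows no overstatement.

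**5. Handling of deaths.** Assume 5-year patency of 75%, 5-year mortality of 20%, and a factor with no effect on patency but a death HR of 2.

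- Hazards per year: λ = −ln(0.75)/5 = 0.0575; μ = −ln(0.80)/5 = 0.0446.
- Formulas: F = λ/(λ+μ) × (1 − e^(−5(λ+μ))) is failure seen before death; S = e^(−5(λ+μ)) is alive and patent.
- Without the factor: F = 0.225, S = 0.60. With it (μ doubled): F = 0.204, S = 0.48.
- Deaths counted as patent: OR = (0.204/0.796)/(0.225/0.775) = 0.88.
- Deaths dropped: OR = (0.204/0.48)/(0.225/0.60) = 1.13.

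At 3 years the pair is 0.93 / 1.07, and at 1 year 0.98 / 1.02. With a 50/50 factor and n = 100, the 5-year bias is at most 0.26 SE, and false rejection is at most 5.8% instead of 5%. A death HR of 4 would be needed to reach about 0.7 SE (11%).

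**6. Power after the change.** ln HR = 2.80/√(24 × 0.25) = 1.14, so 80% power at 24 events needs an HR of about 3.1 for a 50/50 factor. Per SD: 2.80/√24 = 0.57, HR about 1.8.

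**The case against.** The strongest reply is that this is one secondary analysis in a single-arm cohort, that logistic regression is valid at a fixed horizon when every patient's status is known, and that the event counts, correlations, mortality and candidate list are all assumed or reconstructed. Much of this stands. The censoring bias is small at this sample size. The second filter lowers the false-factor rate relative to the screen alone. Cox regression with the same 25 candidates would have the same selection problem: the fall to about 14% comes from testing three factors, not from changing the model. What the reply does not remove is the written selection rule, which performs poorly at every event count and correlation in the table.

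Two stronger readings are tempting. One is that a chance factor is more likely than not. For the rule as a whole that holds clearly only with independent candidates, which is implausible when L2 lies within L4 and the diameters are from neighbouring or paired vessels. With correlation the rate is about half or less.

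The other is that unequal follow-up at the interim looks distorts the model. The document does not say that the factor model is fitted then. The Timeline ties those looks to completed visits: "Months 15-18 Conclusion of recruitment, first (3 months) follow-up end for every patient, ad-interim analysis" and "Month 15-36 12-months follow-up end, mid-term analysis". With enrolment ending at month 15, every patient can reach five years by month 75 (15 + 60), when the final analysis ends.

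**Conclusion.** The point holds, at minor to moderate weight. If followed as written, the rule gives roughly a 36 to 52% chance of reporting at least one spurious factor with correlated candidates (up to about 66% if independent), and it tends to overstate a moderate real one. These figures assume 25 candidates and 12 to 35 failures. The documents give no event rate for this device; the only patency range that they quote, 76 to 98% at one year for kissing stents, would mean 2 to 24 failures per 100 if carried over.

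The mismatch between Kaplan-Meier and logistic regression is real but secondary: its direction depends on handling that the plan leaves open, and its size is small at n = 100.

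A reader might infer that the patency results themselves are unsound, or that the outcome of the factor model is wholly unknown. Neither follows. The Kaplan-Meier estimate does not use this model. Section 7 links the factors to the primary outcomes, so the family is known; what is missing is which of the nine combinations (three patency types by three terms) is modelled.

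**What to change.** In section 8 (Statistical methods), before outcome data are examined:

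- Name the patency type to be modelled, for example primary patency.
- Replace P-value selection with a short prespecified list of anatomical and preoperative factors already collected, sized to the expected number of events.
- Fit these by Cox regression with the same time origin and censoring as the Kaplan-Meier curves. Interpret the hazard ratios as cause-specific, because death competes with loss of patency.
- State how patients who withdraw are censored, and reconcile the end of CRF entry in section 8 with the continued follow-up in section 7.
- Keep logistic regression for fixed-time outcomes such as technical success and 30-day events.
- Report every prespecified factor with its 95% CI whatever its P-value, and label the analysis exploratory.

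The cost is SAP wording and different Stata commands, with no new data. The downside is that only a few factors can be examined, with power only for large effects: at 24 events, an HR of about 3.1 for a 50/50 factor. Cox regression alone, without the shorter list, would leave the main problem in place.

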4. BACKGROUND

In the last two decades there was a general shift from conventional open surgery to endovascular mini-invasive interventions, particularly towards patients with iliac and aortic occlusive disease (AIOD). However, while iliac artery angioplasty and stenting increased of 8.5 fold from 1996 to 2000, aorto-bifemoral bypass fell by only 15%^{1,2}. Indeed, according to ESVS/ESC guidelines open surgery remains the preferred choice for the most complex lesions to address by in endovascular fashion (TransAtlantic Inter-Society Consensus [TASC II] type C and D lesions)³. The reason is the good long-term patency of aorto-bi-iliac or aorto-bifemoral bypass among endovascular devices⁴. Surgery, however, is associated with a high burden of early and late morbidity and mortality, and this aggressive approach is limited by patient's age and comorbidity^{3,4}. In 1991 the kissing stent technique emerged as an alternative for bilateral aortoiliac occlusive disease. Even if the reported technical success rates varied between 89% and 100% with a 1 year primary patency between 76% and 98%, outcomes may be worse in more complex lesions owing to radial size mismatch between stents and certain stent configurations within the distal aorta^{5,6}. In addition, heavy calcified or thrombus filled aorta could increase technical complexity and risk of limb and life-threatening procedural complications such as dissections, aortic rupture and peripheral embolizations. Covered stents may increase patency rates in extensive disease, as shown by the COBEST trial and confirmed in various case series but did not address the problem of a potential radial size mismatch that can lead to re-circulation, turbulence, and stasis of blood, which in turn, may cause thrombus formation and intimal neohyperplasia^{7,8}. Another endovascular procedure for the treatment of AIOD is the CERAB technique. A CERAB is defined as an endovascular reconstruction of the aortic bifurcation using at least one covered stent-graft for the

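### The C-statistic is named as the goodness-of-fit measure, but it shows discrimination only, and with no validation method it would be optimistic after two-step selection in about 100 patients

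*Combined protocol and SAP*

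**What the plan says.** Section 8 (Statistical methods) builds the factor models in stages. Continuous variables are compared first: "differences were tested with the two-sided t-test or the Mann–Whitney U-test, if appropriate". Categorical variables get a chi-square or Fisher test. Then comes the screen: "All data were entered into the logistic regression model if they had a univariable P-value of <0.05". A second filter follows: "Data resulted significant in this model were put in a multivariate one". Results are given as odds ratios with 95% confidence intervals. The check of the models is one sentence: "The goodness of fit of the logistic regression models has been assessed calculating the C-statistic".

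The models serve a secondary endpoint in section 7: "Analysis of anatomical and preoperative factors afflicting the primary outcomes". On numbers, section 7 says "No statistical analysis of the sample size was carried out" and, from caseload and a one-year enrolment, "a sample size of 100 patients was estimated".

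Section 8 names no calibration measure, no bootstrap, cross-validation or other correction for optimism, and no value of C that would count as adequate. The Timeline in section 7 mentions validating the results once, in its last entry. It gives no method and does not tie the word to these models.

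**The concern.** The C-statistic is the probability that a patient with the event has a higher predicted risk than a patient without it. It depends on rank order alone. Goodness of fit asks something else: whether predicted risks agree with observed risks, and whether the shape assumed for each factor is right. The stated check therefore cannot do the job it is given. This is a practical matter here, because many candidate factors are continuous CT measurements (diameters, lengths, calcium and thrombus volumes) for which a curved effect is plausible.

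The second difficulty is where C is computed. The factors pass two significance filters in about 100 patients. If C is then taken from those same patients, it rewards the chance associations that let the factors through. A raised C, presented as good fit, would lend support to anatomical factors that have no effect.

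**Working it through.** The plan has no figure to reproduce. It states no C value, threshold, power or effect size; the only related number is the 100 patients, set by feasibility.

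**Part 1: ranking against fit.**

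C = [R₁ − n₁(n₁+1)/2] / (n₁n₀), where R₁ is the sum of the ranks of predicted risk among the n₁ patients with the event, and n₀ is the number without it. Only ranks enter, so any increasing transformation of the predictions leaves C unchanged.

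Check with 200,000 simulated patients: x standard normal; true logit risk −2.5 + 0.25·exp(1.2x), capped at 4; a logistic model linear in x is fitted. Both models order patients by x, so C is 0.6779 for each. Predicted against observed risk:

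- lowest tenth: 3.3% v 7.8%
- ninth tenth: 22.0% v 16.5%
- highest tenth: 33% v 42%

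This misfit is present in the fitting data, and C does not show it.

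**Part 2: apparent C after selection.**

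Inputs:

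- Patients: 100 (section 7, Sample size).
- Patency losses: assumed 10, 15 or 24. No rate for this device is given. Section 4 gives "1 year primary patency between 76% and 98" per cent for kissing stents, so losses of 100 − 98 = 2 to 100 − 76 = 24 per 100. With 2 events a model could hardly be fitted.
- Candidate factors: assumed 27, range 15 to 40. The count is about 16 CT measures, 7 demographic and comorbidity items, and Rutherford, WIfI, ABI and TASC class: 16 + 7 + 4 = 27.
- All factors are independent and have no effect; about two thirds are continuous (t-test) and the rest binary (Fisher).
- Selection: univariable P < 0.05; joint logistic model; terms with P < 0.05 kept; refit. The plan gives no level for the second step; 0.05 is assumed.

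The nominal chance of at least one false hit at the first screen is 1 − 0.95^k: 54%, 75% and 87% for k = 15, 27 and 40. Simulation of both steps, 1,000 null studies per row:

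| Factors | Losses | Final model kept | Mean apparent C | C ≥ 0.70, of kept models | C ≥ 0.70, of all studies |
|---|---|---|---|---|---|
| 15 | 10 | 44% | 0.736 | 72% | 32% |
| 15 | 15 | 50% | 0.705 | 43% | 22% |
| 15 | 24 | 42% | 0.670 | 23% | 10% |
| 27 | 10 | 60% | 0.746 | 76% | 46% |
| 27 | 15 | 65% | 0.718 | 54% | 35% |
| 27 | 24 | 65% | 0.684 | 35% | 23% |
| 40 | 10 | 71% | 0.768 | 83% | 58% |
| 40 | 15 | 77% | 0.733 | 60% | 47% |
| 40 | 24 | 77% | 0.701 | 49% | 38% |

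The same models scored on 2,000 new patients have mean C of 0.499 to 0.501 in every row. The optimism is thus about 0.67 − 0.50 = 0.17 to 0.77 − 0.50 = 0.27.

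Separate runs with 25 independent factors and both steps kept a final model in about 50%, 62% and 61% of studies (10, 15, 24 losses), and in a repeat in about 53–60%. Mean C was 0.74, 0.71 and 0.68 each time. With an assumed correlation of 0.6 among 12 factors, the rate fell to about 40–46%, and C ≥ 0.70 occurred in 9–25% of all studies.

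**The case against.** The strongest reply is that this is a mislabel in an exploratory association analysis. The plan reports odds ratios with confidence intervals, intends no risk score, and sets no C threshold, so calibration and optimism correction import standards meant for prediction models. Part of this stands: it limits the weight of the point. It does not make the sentence correct, because the plan itself promises an assessment of fit and names a measure that cannot supply one.

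Several stronger readings are tempting, and the documents do not support them.

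- *Noise models will be reported as good.* No cut-off is set. At an assumed 0.70, 10–58% of all null studies reach it, and 23–58% end with no model at all.
- *The plan states that it uses the apparent C.* It does not. This is inferred from the absence of any validation method.
- *C would hide predictions that are wrong on average.* Shifting every predicted risk does leave C unchanged, but a maximum-likelihood logistic model with an intercept matches the mean observed risk in its own data. In the fitting data the relevant misfit is functional form, as in Part 1.
- *The first screen alone gives the size of the problem.* With 25 noise factors, 64–71% of studies pass at least one factor at that screen, but the plan filters twice.
- *C is the only safeguard, and false factors will steer patient selection.* Confidence intervals are also reported, and no selection rule is planned.

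It is also true that noise factors are retained because of significance screening with few events, not because of the C-statistic sentence.

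**Conclusion.** The point holds in limited form. That C measures discrimination and not fit is a matter of definition and needs no assumption about this trial. That the reported C would be optimistic rests on the inference that it is computed in the selection data.

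The size rests on assumed event counts, factor numbers and independence. With 25 to 27 factors, roughly 50–65% of null studies keep a final model, with mean apparent C of about 0.74–0.75, 0.71–0.72 and 0.68 at 10, 15 and 24 losses, against a true 0.50. Over 15 to 40 factors the ranges are 42–77% and 0.67–0.77. Correlated CT measures would lower the retention rate. Noise models can therefore often appear to perform well. The effect is confined to a secondary endpoint; the primary Kaplan-Meier analysis of patency is untouched. The sentence should be corrected because it states a wrong measure and the correction is cheap.

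**What to change.** Replace the sentence in section 8 with:

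> Discrimination will be given as the C-statistic, and fit by a calibration plot (with a check of linearity for continuous factors) and calibration slope. The C-statistic and slope will be corrected for optimism by bootstrap repeating every selection step; resamples that select no factor count as C = 0.50, and the number with no factor or with separation will be reported.

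The optimism correction is needed for the slope as well as for C, because the slope of a maximum-likelihood logistic fit in its own data is 1 by construction.

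The cost is SAP wording and modest Stata code, with no new data or patients. The reported C will be lower, and the slope will be unstable when events are few. The change corrects the reported performance; it does not itself stop noise factors from being selected. That would need a short, pre-specified factor list matched to the expected number of events.
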